**Mitigating ethnic disparities in access and engagement in spine pain rehabilitation –
STEPPT Mixed Methods Pilot Study**

NCT06835439

(May 23, 2025)

Study Objectives

The purpose of this pilot study is to assess the feasibility, acceptability, and preliminary effectiveness of the STEPPT intervention to improve ethnic disparities in physical therapy referral and adherence between Hispanic and Non-Hispanic White patients with spine pain. We expect the intervention will be feasible and acceptable, with suggested modifications from patient and clinic staff stakeholders that will inform a larger clinical trial. Compared to standard care, we expect STEPPT to reduce ethnic disparities in physical therapy referral and adherence outcomes.

Design & Methods

STEPPT is a health system, quality improvement intervention. Our research team developed the preliminary STEPPT intervention based on available evidence, to promote physical therapy referral and attendance for Hispanic patients with spine pain. Our team then adapted the STEPPT intervention based on insights gained from feedback from Federally Qualified Health Center (FQHC) administrators and co-development workshops conducted with FQHC clinic directors, primary care physicians, nurses, medical assistants, and patient health navigators. The pilot single-arm clinical trial will allow our research team to implement and assess the adapted STEPPT intervention in a single FQHC clinic prior to initiating a larger clinical trial.

Participant Eligibility and Enrollment

Because this is a health system quality improvement intervention, all patients at the FQHC pilot clinic will be included in the study if they: (1) are 18 years of age or older, (2) identify as Hispanic or Non-Hispanic White ethnicity/race, (3) have signed a broad consent for use of de-identified health information for research, and (4a) identify a new spine pain problem at a visit with a primary care physician (new diagnosis of neck or back pain added to the problem list during the visit) OR (4b) have an existing spine pain problem (existing diagnosis of neck or back pain on the problem list) and their physician generates any referral for the spine problem at the visit. Patients with a possible non-musculoskeletal etiology for spine pain (e.g. infection, cancer, urological disorder, pregnancy) or conditions requiring urgent medical intervention (e.g. fracture, cauda equina syndrome) will be excluded.

Upon completion of the STEPPT pilot study, the research team will conduct post-intervention interviews with a purposive sample of Hispanic patients who meet study eligibility criteria. Participants will be contacted via phone by Research staff who are FQHC

employees or who are onboarded as FQHC volunteers to offer them the opportunity participate in interviews. To ensure a diverse and representative sample, we will purposively sample 20 participants based on age, sex, pain region (low back, neck), language preference, and referral and adherence status. Participants who agree to participate in interviews will be scheduled for an in-person or Zoom interview based on their preference.

Informed Consent

A waiver of consent was granted for enrollment in the STEPPT pilot intervention because it meets the requirements outlined in 45 CFR 46.116, section f3 i) the research involves no more than minimal risk to the subjects, ii) the research could not practicably be carried out without the requested waiver or alteration, iii) only patients who have signed the a broad consent for use of de-identified health information from the electronic health records will be included in the study, iv) the waiver will not adversely affect the rights and welfare of the subjects. The STEPPT intervention is a minimal risk health systems quality improvement intervention including education and enhanced care navigation to improve physical therapy referral and adherence to physical therapy for Hispanic/Latino patients with neck /back pain. No additional pertinent information will be provided to subjects after participation as it would be impractical to do so, however, if effective the approaches will be implemented more broadly across the health system.

Patients who agree to participate in post-intervention interviews will be asked to provide written informed consent prior to participation in the interview. Bilingual study team members will obtain written informed consent from participants and then conduct the interviews.

STEPPT Pilot Intervention

The pilot STEPPT intervention includes: (1) auto-referrals to physical therapy in the electronic health records (EHR) system, (2) delivery of health literacy materials through multiple channels (after visit summary, text message, link to educational video, etc.), and (3) enhanced health care navigation. Prior to commencing the pilot trial, STEPPT research staff will conduct trainings with clinic staff including medical providers (primary care provider (PCP), nurse, medical assistant (MA)) and study patient health navigators.

Auto-Referrals to Physical Therapy: The first component of the STEPPT intervention is an auto-generated physical therapy referral in the EHR system for all patients with a new low

back or neck pain problem (added to the problem list at the physician visit). The physician must sign the auto-referral before the patient can be scheduled for physical therapy. During STEPPT intervention, Non-Hispanic White (NHW) participants with a new spine pain problem will also receive an auto-generated PT referral (similar to Hispanic participants) based on administrator and health system preferences.

Patient Education Materials: Patient education materials that were developed include: (1) neck/back pain fact sheet, (2) information on what to expect in physical therapy for neck/back pain and the FQHC physical therapy referral and scheduling process, (3) instructions on postural exercises for spine pain relief, and (4) an educational video on how physical therapy can help with neck/back pain and information on physical therapy services at the FQHC. These materials have been culturally tailored for Hispanic patients and are available in both English and Spanish, based on patient-preferred language. These materials will be delivered via two different channels to Hispanic patients with a new or existing spine pain problem who are referred to physical therapy. First, the custom EHR system will be leveraged to auto-order printed education materials (#1-3) for Hispanic patients, to be included in the “After Visit Summary” provided to the patient by the nurse or medical assistant. Second, electronic copies of the education materials (#1-3) and a link to the educational video (#4) will be sent via automated text message within 24 hours of the physical therapy referral. Patients will be encouraged to share and discuss these informational resources with their family members to solicit social support for engaging in physical therapy. During STEPPT intervention, NHW participants with a new or existing spine pain problem will only receive education materials that are ordered by their physician. Consistent with current practices at FHCS, the neck/back pain fact sheet will be the only education material that will be available for physicians to order for NHW patients.

Enhanced Healthcare Navigation: Enhanced healthcare navigation will be administered by the STEPPT Patient Health Navigators (PHN) utilizing the STEPPT Registry, an interface within the HIPAA-protected FQHC network, specifically tailored to track and provide personalized enhanced care navigation to Hispanic participants. The study PHN will contact each participant individually. First, they will provide a brief (~1-2 min) semi-scripted explanation of how physical therapy can help patients manage their pain and improve function. This will help reinforce the health literacy component of STEPPT by providing information about the benefits of physical therapy from multiple sources. Next, the PHN will schedule the patient for their first physical therapy visit, at a time and location that is convenient for the patient. Last, the PHN will ask the patient if they anticipate any challenges to attending physical therapy, proactively assist the patient in developing a plan to overcome any identified barriers and will refer the patient to additional resources (e.g.,

transit, childcare, etc.) as necessary. If needed, the PHN can also manually deliver a follow-up text message with a link to electronic educational materials. To address linguistic barriers, all STEPPT PHNs will be bilingual (Spanish/English). During STEPPT intervention, NHW patients who are referred for physical therapy will be contacted by centrally located FQHC staff who will process the referral and reach out to the patient to schedule an appointment consistent with current practice.

Standard Care Control

Standard Care reflects the existing care coordination pathway at the FQHC and will serve as the control condition. During standard care, a centrally located Referral Specialist will verify insurance authorization when a physical therapy referral is made, and three call attempts will be made to schedule the PT evaluation. If no contact is made after 30 days, a letter will be sent to inform the patient that they are responsible for calling the clinic to follow up on the referral. During Standard Care, the FQHC providers and staff will not receive any education on the benefits of physical therapy referral for spine pain or culturally responsive strategies to facilitate patient engagement. Consistent with standard practice, patients will only receive a fact sheet on neck or back pain if manually ordered by their PCP and will not receive personalized enhanced care navigation.

Outcomes

Physical Therapy Referral and Adherence Rates (Primary)

The primary outcomes that will be gathered from the electronic health record (EHR) are rates of physician referral to physical therapy (within 3 months of index visit) and patient adherence to physical therapy referral (within 6 months of referral) for spine pain before (3-month baseline) and after (3-month intervention) implementation of STEPPT. Patient sociodemographic characteristics will also be collected from the EHR for descriptive purposes.

Involvement Rating

During STEPPT intervention, a formal process evaluation also will be conducted by the study team to assess clinic involvement in STEPPT training and implementation activities. The study team will conduct monthly audits including reviews of data from all levels of the STEPPT program, and structured observations of the clinic workflow. Process evaluation measures will include a quantitative Involvement Rating Score (range 0 to 11 points, with higher scores indicating greater involvement in STEPPT implementation), supplemented by the qualitative analysis of structured observations and field notes. Based on this evaluation, the research team will provide monthly feedback to clinic staff, which will include a summary report of progress toward equitable rates of physical therapy referral

and adherence. Research staff will support uptake and adherence to STEPPT with regular outreach to FQHC clinic staff to share lessons learned, help problem-solve barriers, and suggest customized strategies.

Patient Interviews

The study team will conduct post-intervention interviews with a subsample of participants to evaluate acceptability and feasibility of the STEPPT intervention. A semi-structured interview guide with open-ended questions was developed using the Reach, Effectiveness, Adoption, Implementation, and Maintenance (RE-AIM) Framework. The interview guide includes questions regarding Hispanic patients' opinions of the materials they received during the pilot intervention, the delivery of the materials, and their experience receiving Enhanced Care Navigation. Interviews will take approximately one hour and will be conducted in the patient's preferred language by trained moderators.

Interviews will be audio-recorded and transcribed for qualitative analysis. Patient recommendations identified in the interviews will inform the need for additional adaptations before finalizing the STEPPT intervention procedures and materials prior to a larger clinical trial.

Data Processing and Storage: All participant data will be retained in the password-protected, HIPAA-compliant FQHC system. Power BI will be used to extract participant data from EHR and referral systems, and a registry will be used to track participants for enhanced care navigation. Only research team members who are employees or onboarded volunteers at the FQHC, and who have met all HIPAA and patient privacy training requirements, will have access to these data. When participant data are exported from the FQHC system for analysis, data will be coded by an FQHC Data Scientist using a unique identifier such that only deidentified data will be shared and used for analysis. De-identified data that is shared will be stored on password-protected HIPAA-compliant servers at San Diego State University. A Data and Safety Monitoring Plan will be implemented to maintain the safety and confidentiality of all study participants and to ensure data integrity.

Statistical Analysis Plan

The primary outcome of interest is the change in rates of referral and adherence to physical therapy before and after the STEPPT intervention between Hispanic and NHW participants with spine pain, which will define the overall effect of STEPPT on ethnic disparities. Descriptive statistics will be summarized at each time point (baseline vs. intervention) separately for each group (Hispanic vs. NHW). Effect size estimates for change in referral

and adherence rates before and after intervention will be calculated to conduct a power analysis for a larger clinical trial of the STEPPT intervention.

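### Criterion 4b admits existing-pain patients only when a referral is made, so in that stratum the primary referral rate is conditional on referral and can distort the disparity change

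*Combined protocol and SAP*

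**What the plan says.** Participant Eligibility and Enrollment gives two routes into the study.

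- Route 4a needs only a "new diagnosis of neck or back pain added to the problem list during the visit"; no referral is required.
- Route 4b is for patients whose diagnosis is already on the problem list. They enter only if "their physician generates any referral for the spine problem at the visit". The wording covers any type of referral, so a PT referral qualifies and so does any other.

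Under Outcomes, the first primary outcome is "rates of physician referral to physical therapy (within 3 months of index visit", and the second is "patient adherence to physical therapy referral (within 6 months of referral". Both are compared "before (3-month baseline) and after (3-month intervention) implementation of STEPPT".

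The Statistical Analysis Plan takes as its target the "change in rates of referral and adherence to physical therapy before and after the STEPPT intervention between Hispanic and NHW participants". It states no denominator for the referral rate and makes no distinction between 4a and 4b. The resulting effect sizes are to be used to power a larger trial.

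The auto-referral described under STEPPT Pilot Intervention applies to new problems only, in both ethnic groups: "Non-Hispanic White (NHW) participants with a new spine pain problem will also receive an auto-generated PT referral".

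**The concern.** For an existing-pain patient, a PT referral at the visit does two things at once: it brings the patient into the study and it scores a success. An existing-pain patient whose physician makes no referral has no qualifying visit and never enters the denominator. Yet non-referral is the access failure the study sets out to measure.

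Denominator membership in this stratum therefore depends on physician behaviour, which can differ between Hispanic and NHW patients. It can also differ between periods. STEPPT adds clinic staff training and monthly feedback on equitable PT referral (STEPPT Pilot Intervention; Involvement Rating), while standard care has no provider education on PT referral (Standard Care Control). If the denominator shifts, the before-after change in the disparity can move for reasons unrelated to how many patients are sent to PT. An error here carries into the planning of the larger trial, and enrolling more patients would not remove it.

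**Working it through.** The documents state no sample size, referral rate or 4a/4b mix, so there is no figure to reproduce. The check asks what the entry rule does to the rate under assumed values.

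**Inputs.** From the documents: the two entry rules, the referral outcome, and the comparison by period and ethnicity. Assumed:
- p = probability of a PT referral at an existing-pain visit
- q = probability of a non-PT referral only at such a visit
- w = existing-pain share of all spine visits
- PT referral rate in new-problem patients = 30% in every group and period

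Only referrals made at the visit are counted.

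**Formulas.**
- 4b stratum: true rate p; rate under the entry rule p/(p+q).
- 4a and 4b pooled: true rate (1−w)×0.30 + w×p; rate under the entry rule [(1−w)×0.30 + w×p] / [(1−w) + w×(p+q)].

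**Scenario A, a real improvement is hidden.** Hispanic p/q goes from 20/20% to 40/40%; NHW is 40/40% throughout. Every 4b rate is 50%, so a true gap reduction of 20 points in the stratum shows as 0. Pooled at w = 50%:
- True: Hispanic 0.15 + 0.10 = 25%, NHW 0.15 + 0.20 = 35%. The gap of 10.0 points falls to 0.
- Observed before: Hispanic 0.25/0.70 = 35.7%, NHW 0.35/0.90 = 38.9%. The gap of 3.2 points falls to 0.

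**Scenario B, an improvement is manufactured.** Hispanic p/q goes from 20/20% to 20/10%; NHW is 40/20% throughout. The true gap does not change. Pooled at w = 50%:
- Observed before: Hispanic 0.25/0.70 = 35.7%, NHW 0.35/0.80 = 43.8%; gap 8.0 points.
- Observed after: Hispanic 0.25/0.65 = 38.5%, NHW 43.8%; gap 5.3 points.
- Apparent reduction 2.7 points against a true 0.

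**Dependence on the mix (gap reduction, points).**

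| w | A true | A observed | B true | B observed |
|---|---|---|---|---|
| 25% | 5.0 | 1.9 | 0 | 1.0 |
| 50% | 10.0 | 3.2 | 0 | 2.7 |
| 75% | 15.0 | 3.2 | 0 | 6.5 |

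**Substitution of PT for other referrals.** Any-referral rate 50% in every cell; Hispanic p/q from 20/30% to 30/20%, NHW 35/15%. In the 4b stratum a true 10-point reduction shows as 20 (Hispanic 40% to 60%, NHW 70%). Pooled at w = 50%, a true 5.0 shows as 0.30/0.75 − 0.25/0.75 = 6.7.

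**Where the distortion is small.** Let q be equal in all cells, Hispanic p rise from 20% to 30%, and NHW stay unchanged. The true reduction in the 4b stratum is 10.0 points. The observed reduction is 0 at q = 0, 5.7 at 5%, 8.3 at 10%, 10.0 at 20%, 10.0 at 30% and 9.5 at 40%. Pooled at w = 50% and q = 20%, a true 5.0 shows as 0.30/0.75 − 0.25/0.70 = 40.0% − 35.7% = 4.3.

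**The case against.** The other side has several fair points.

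- A reader might infer that 4b patients are selected on the outcome itself and are all successes. The text does not support that. Entry is on any referral, a wider event than PT referral, and the 4b rate is fixed at 100% only if PT is the sole referral type used. A conditional rate can still differ by ethnicity.
- A reader might also infer that the whole referral rate is uninformative about access or disparity. That goes too far. 4a patients enter without a referral and are the only ones who get the auto-referral, so their part of the rate is not selected this way.
- Pooling is inferred. The analysis plan does not announce a pooled rate; it leaves the denominator undefined.
- The outcome window is three months, so a 4b patient who enters through another referral can still become a success. The p/(p+q) formula is an approximation.
- Scenario B needs other referrals to fall without PT taking their place, and no section describes a mechanism for that.
- The any-referral condition may be meant to pick out visits at which the spine problem was actually addressed.
- This is a single-clinic pilot with descriptive statistics and no hypothesis test.

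These points limit the claim but do not remove it. Under full substitution, the more natural mechanism, the change is still distorted, upwards. The three-month window does not bring back patients who were never admitted. And the plan specifies no report that would show which situation applies.

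**Conclusion.** The concern holds in conditional form. In the 4b stratum the primary referral rate is approximately the proportion going to PT among those referred, and unreferred existing-pain patients are missing from it. Because the plan compares rates among participants without separating 4a from 4b, the before-after Hispanic versus NHW change can be hidden, manufactured or exaggerated.

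That it will be distorted is not established. The size rests on p, q and w, none of which the documents give. In the pooled illustrations at w = 50%, the results run from 3.2 observed against 10 true, through 2.7 against 0 and 6.7 against 5.0, to 4.3 against 5.0. Within the 4b stratum the bias is nil at some values. The adherence outcome is defined among those referred and does not share the flaw.

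**What to change.** In the outcome definition and the Statistical Analysis Plan:

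1. Make 4a (new-problem) patients the population for the primary referral rate, and for the referral effect size used to power the larger trial, in both periods and both ethnic groups.
2. Report the 4b referral rate separately, labelled as conditional on any referral, with counts by ethnicity and period.
3. Keep 4b patients in the adherence outcome, reported by stratum.
4. Report the number of 4a entries by ethnicity and period. Adding a new problem to the list triggers the auto-referral during the intervention, so recording of new problems could itself change.
5. If referral in existing pain is of interest, use as denominator the visits at which the existing spine problem was addressed, whether or not a referral was made, provided the EHR can identify them. Counting every primary care visit by a patient with an existing spine diagnosis would bring in visits unrelated to the spine, where non-referral is not a failure.

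Items 1 to 4 need wording changes and an EHR query that flags the entry route; care delivery does not change. The cost is fewer patients in the referral analysis, and so a less precise effect size.

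### Adherence among referred patients is conditional on a step that STEPPT changes, so its change needs an all-eligible companion rate and a new/existing split

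*Combined protocol and SAP*

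**What the plan says.** Under Physical Therapy Referral and Adherence Rates (Primary), the protocol names two outcomes. One is the rate of physician referral to physical therapy (PT) within 3 months of the index visit. The other is "patient adherence to physical therapy referral (within 6 months of referral) for spine pain before (3-month baseline) and after (3-month intervention"). Neither a denominator nor an attendance threshold is written for adherence.

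Under Auto-Referrals to Physical Therapy, "The first component of the STEPPT intervention is an auto-generated physical therapy referral in the EHR system" for patients with a new problem. NHW patients with a new problem "will also receive an auto-generated PT referral (similar to Hispanic participants"). A physician must sign it before scheduling, so a rise in referral is intended but not automatic.

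The two entry routes differ (Participant Eligibility and Enrollment). New-problem patients (4a) need no referral to enter. Existing-problem patients (4b) enter only if "their physician generates any referral for the spine problem at the visit".

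The other components could also act on referral or attendance:
- Materials go "to Hispanic patients with a new or existing spine pain problem who are referred to physical therapy", and navigation is for Hispanic participants.
- Before the pilot, "STEPPT research staff will conduct trainings with clinic staff including medical providers", whereas in standard care "the FQHC providers and staff will not receive any education on the benefits of physical therapy referral for spine pain".
- During the intervention the team "will provide monthly feedback to clinic staff, which will include a summary report of progress toward equitable rates of physical therapy referral" and adherence.

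The Statistical Analysis Plan takes the before-after change in both rates, compared between Hispanic and NHW participants, as the overall effect on disparities. It summarises by period and ethnicity only. There is no attendance rate for all eligible patients and no 4a/4b split.

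**The concern.** On the natural reading, adherence is measured only in patients who pass a step that the intervention itself alters. In the intervention period, the referred 4a patients can include people who would not have been referred at baseline. If these added patients attend at a different rate, adherence among the referred moves even when nobody's behaviour changes. The NHW comparison removes this only if the added share times the attendance shortfall is equal in the two groups. The study's premise is that referral differs by ethnicity, so equality cannot be taken for granted.

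What is at stake is how the pilot's adherence result is interpreted. The gap could shrink, or fail to shrink, partly because of who was referred. That shift is a legitimate part of the package effect, but the planned tables give no way to see it.

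**Working it through.** **Inputs.** The documents give no referral rate, adherence rate or sample size, so there is no plan figure to reproduce. Every rate below is an assumption.

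- 4a referral: Hispanic 40% to 80%, NHW 60% to 80% (full uptake); or 40% to 60% and 60% to 70% (partial uptake).
- Baseline adherence among the referred: Hispanic 45%, NHW 60%, a gap (NHW minus Hispanic) of 15 points.
- x = points by which added patients attend less often than those referred either way.
- n = points that navigation and materials add for every referred Hispanic patient.
- Patients referred at baseline rates would still be referred, and there is no time trend.

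**Step 1: added share of referred 4a patients**, A = (r1 − r0)/r1, where r0 and r1 are referral before and after.
- Full uptake: Hispanic (80 − 40)/80 = 50%; NHW (80 − 60)/80 = 25%.
- Partial uptake: Hispanic 20/60 = 33.3%; NHW 10/70 = 14.3%.

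**Step 2: distortion of the 4a adherence gap** = A(Hisp) × x(Hisp) − A(NHW) × x(NHW). Positive means the gap looks wider.

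| Scenario | Distortion (points) |
|---|---|
| Full uptake, x = 15 | 0.25 × 15 = 3.75 |
| Full uptake, x = 30 | 0.25 × 30 = 7.5 |
| Full uptake, x = 0 | 0 |
| Full uptake, x = −15 (added patients attend more) | −3.75 |
| Partial uptake, x = 15 and 30 | 0.19 × x = 2.9 and 5.7 |
| Full uptake, x = 15 Hispanic, 30 NHW | 7.5 − 7.5 = 0 |
| Full uptake, x = 30 Hispanic, 15 NHW | 15 − 3.75 = 11.25 |

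**Step 3: pooled 4a + 4b, as the plan would report it.** Let s be the 4a share of referred patients in the intervention period. Assume s is the same in both ethnic groups, baseline adherence is equal in 4a and 4b, and 4b referral does not shift. The distortion is s × 0.25x:
- s = 0.4: 1.5 (x = 15) and 3.0 (x = 30).
- s = 0.8: 3.0 and 6.0.

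If training and feedback also add 4b referrals (assumed added shares 20% Hispanic, 10% NHW), the distortion is x × [0.25s + 0.10(1 − s)]: 2.4 and 4.8 at s = 0.4; 3.3 and 6.6 at s = 0.8.

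**Step 4: can the two rates point in opposite directions?** Within 4a, full uptake, n = 5, x = 30:
- Referred-only: Hispanic 45 + 5 − 15 = 35; NHW 60 − 7.5 = 52.5. The gap goes from 15 to 17.5.
- Per 100 eligible, before: 0.40 × 45 = 18 and 0.60 × 60 = 36, gap 18. After: 0.80 × 35 = 28 and 0.80 × 52.5 = 42, gap 14.

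So the referred-only gap widens while the per-eligible gap narrows and Hispanic attendance rises from 18 to 28. Within 4a the referred-only gap widens when 0.25x > n, that is x > 4n. At n = 10 and x = 30 it is 15 − 10 + 7.5 = 12.5, so it narrows.

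**Step 5: does the reversal carry over to the pooled rate?** With n = 5 and x = 30 the pooled gap is 15 − 5 + 7.5s, which exceeds 15 only if s > 5/7.5, about two-thirds. With the assumed 4b shift it is 15 − 5 + 3 + 4.5s, which exceeds 15 only if s > 2/4.5, about 44%. At s = 0.4 the gap does not widen in either case.

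**Step 6: the companion cannot stand alone either.** With n = 0 and x = 0, the per-eligible gap falls from 18 to 0.80 × 60 − 0.80 × 45 = 12 through referral alone, while the referred-only gap stays at 15.

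**The case against.** **The plan does not read adherence alone.** The SAP names the change in referral and adherence together, and nowhere attributes the adherence change to navigation and materials. This stands: a reader might infer that the plan makes that attribution, and it does not. But it also gives no guidance on reading the two changes together.

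**Referral is co-primary, so a reader can multiply.** Partly stands. In Step 4 a reader would see Hispanic referral double beside the adherence change. The product is not planned, however, and for pooled rates it is only approximate, because 4b patients enter only after a referral of some kind. It is clean only in 4a, which needs the split.

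**NHW patients get the auto-referral too.** It cancels only under equality of share times shortfall. One row in Step 2 shows exact cancellation, and others do not.

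**The denominator is a reading.** Stands. If all participants were meant, a per-participant rate would already be primary. Stating the denominator settles this.

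**The effect is small against noise.** Assuming 50 referred patients per period-by-ethnicity cell and rates near 50%, the standard error of the before-after ethnic contrast is √(4 × 0.25/50), about 14 points; at 200 per cell, about 7. Stands as a reason for low priority. It does not settle what the estimate means.

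A reader might also infer that the larger trial's sample size would be wrong. The documents do not support that: a trial with the same package and outcome would show the same kind of shift.

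**Conclusion.** The point holds as an inexpensive improvement to consider, with medium confidence. The plan's adherence change is, on its natural reading, conditional on a variable that the intervention alters, and the planned tables do not let a reader separate engagement from the change in who is referred. Under the assumed rates the distortion is about 0.25 times the shortfall within 4a, and 1.5 to 6 points pooled under the assumptions of Step 3 without a 4b shift. It can be zero or negative, and neither direction nor size can be learned from the documents.

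A reader might infer that the planned adherence gap would generally appear to widen under a helpful intervention. That is not supported. With a real navigation gain, the reversal is shown only within 4a, at a 30-point shortfall and a 5-point navigation effect. The pooled rate would need a 4a share above about two-thirds, or about 44% with the assumed 4b shift.

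**What to change.** In the primary outcome section and the SAP:

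1. Keep adherence among the referred as primary. State that denominator, and state the attendance threshold, which the plan does not give.
2. Co-report, by period and ethnicity, the proportion of all eligible 4a patients with a PT referral signed within 3 months of the index visit and PT attended, at the same threshold, within 6 months of that referral.
3. Tabulate adherence separately for 4a and 4b. Hispanic 4b patients referred to PT receive the materials but no auto-generated referral, so their adherence is less exposed to the shift. Note that 4b entry requires a referral of some kind, and that training and feedback may still change PT referral there.
4. Add one sentence: the referred-only change is to be read together with the all-eligible rate.

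Cost: no new data, only the same EHR fields and the new/existing flag already used for eligibility. The downsides are one more outcome, which combines referral with attendance and so does not isolate navigation, and small, imprecise 4a/4b cells in a single clinic.
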